5.5 Laboratory Assessments

Laboratory panels are composed of the following:

Hematology		

 WBC count with differential (including at minimum: neutrophils, basophils, eosinophils, lymphocytes, monocytes) 	
 hematocrit platelet count RBC count hemoglobin 	
Serum chemistry		

 albumin ALP amylase ALT AST bicarbonate BUN chloride 	
 creatinine GGT Glucose (fasted) calcium lactate dehydrogenase lipase CRP 	
 magnesium phosphorus potassium sodium total bilirubin total protein
Urinalysis		

 appearance color pH specific gravity ketones protein UPCR 	
 glucose bilirubin nitrite creatinine urobilinogen 	
 occult blood (microscopic examination of sediment will be performed only if the results of the urinalysis dipstick evaluation are positive)
Other		

 TSH, Free T3 and Free T4 Pregnancy text (urine or serum) for women of child-bearing potential 		
 PT/INR or PTT

ALP, alkaline phosphatase; ALT, alanine aminotransferase; AST, aspartate aminotransferase; BUN, blood urea nitrogen; ESR, erythrocyte sedimentation rate; GGT, γ -glutamyltransferase; INR, International Normalized Ratio; PT, prothrombin time; PTT partial thromboplastin time; RBC, red blood cell; TSH, thyroid stimulating hormone; UPCR, urine protein/creatinine ratio; WBC, white blood cell; CRP, C-reactive protein

Abnormalities in clinical laboratory tests that lead to a change in subject management (eg, dose delayed [withheld] or reduced, requirement for additional medication, treatment or monitoring) are considered clinically significant for the purposes of this study, and will be recorded on the Adverse Events Case Report Form (CRF). If laboratory values constitute part of an event that meets criteria defining it as serious, the event (and associated laboratory values) must be reported as an SAE.

5.6 Tumor Assessment

5.5.1 Efficacy Assessments

Objective response rate (ORR) is the primary endpoint for this study which will be evaluated using RECIST 1.1 criteria (14). Evaluation of response will follow the Response Evaluation Criteria in Solid Tumors (RECIST 1.1). All tumor measurements must be recorded in centimeters.

For the purposes of this study, patients should be re-evaluated for response at 12 weeks. This will be obtained after last dose of cabozantinib before surgical resection while waiting 28 days wash-out period. In addition to week 12 scan, week 6 scan should also be obtained to rule out rapid progression. Only scans at week 12 (prior to surgery) will be used for purposes of the primary objective. In order to have better response assessment, we will use same type of scan at baseline and at 12 weeks. Since patients are required to be non-metastatic disease patients, likely only target lesion assessment will be needed.

- **Target Lesions:**

All measurable lesions up to a maximum of two lesions per organ and 5 lesions in total, representative of all involved organs, should be identified as target lesions and recorded and measured at baseline. Lymph nodes must be at least 15mm in short axis to be included as a target lesion. Target lesions should be selected on the basis of their size (those with the longest diameter) and their suitability for accurate repeated measurements (either by imaging techniques or clinically). A sum of the longest diameter for all target lesions will be calculated and reported as the baseline sum longest diameter. The baseline sum of longest diameters will be used as the reference by which the objective tumor response is characterized.

- **Non-target Lesions:**

All other lesions (or sites of disease) should also be recorded at baseline. Measurements of these lesions are not required, but the presence or absence of each should be noted throughout follow-up.

5.5.2 Evaluation of Target Lesions:

- **Complete Response (CR):**

The disappearance of all target lesions.

- **Partial Response (PR):**

At least a 30% decrease in the sum of the longest diameter of target lesions, taking as reference the baseline sum longest diameter.

- **Progressive Disease:**

At least a 20% increase in the sum of the longest diameter of target lesions, taking as reference the smallest sum longest diameter recorded since the treatment started or the appearance of one or more new lesions.

- Stable Disease:

Insufficient shrinkage to qualify for partial response, or insufficient increase to qualify for progressive disease, taking as reference the smallest sum longest diameter since the treatment started.

5.5.3 Evaluation of Non-target Lesions:

- Complete Response:

The disappearance of all non-target lesions.

- Incomplete Response/Stable Disease:

The persistence of one or more non-target lesion(s)

- Progressive Disease:

The appearance of one or more new lesions and/or unequivocal progression of existing non-target lesions.

- Evaluation of Best Overall Response: (see table below)

Evaluation of Best Overall Response (RECIST)

Target Lesions	Non-Target Lesions	New Lesions	Overall Response
CR	CR	No	CR
CR	Non-CR/Non-PD	No	PR
CR	Not evaluated	No	PR
PR	Non-CR/Non-PD/not evaluated	No	PR
SD	Non-CR/Non-PD/not evaluated	No	SD
PD	Any	Yes or No	PD
Any	PD***	Yes or No	PD
Any	Any	Yes	PD

* See RECIST 1.1 manuscript for further details on what is evidence of a new lesion.
 
*** In exceptional circumstances, unequivocal progression in non-target lesions may be accepted as disease progression.
 
Note: Patients with a global deterioration of health status requiring discontinuation of treatment without objective evidence of disease progression at that time should be reported as “symptomatic deterioration.” Every effort should be made to document the objective progression even after discontinuation of treatment.
			

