- If the subject does not recover from his or her toxicities to tolerable Grade ≤ 2 within 6 weeks, the subject will have study treatment discontinued unless there is unequivocal evidence that the subject is benefitting. In this situation, a subject may be able to restart therapy with a dose reduction upon resolution of the toxicity and with agreement of the principal investigator;
- Request by regulatory agencies for termination of treatment of an individual subject or all subjects under the protocol;
- Significant noncompliance with the protocol schedule in the opinion of the investigator;
- Subjects who cannot tolerate the minimum protocol-specified dose of study treatment will have study treatment discontinued;
- Progressive disease (PD) or the subject no longer experiences clinical benefit as determined by the investigator

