^gPatients will undergo kidney surgery min 28 days after the last dose of cabozantinib.

^hAppendix C

ⁱAppendix D

^jIf clinically indicated

^kBlood collection post-surgical resection for correlative studies

^lOnly from female patients with child bearing potential within 72 hours of study drug

^mThese assessments may be done within 14 days of Week 1 Day 1, prior to releasing the cabozantinib.

ⁿThis scan can be done within 28 after last dose of cabozantinib

If the subject is unable to have a study assessment taken within the defined time window due to an event outside of his or her control (eg, clinic closure, personal emergency, inclement weather, vacation), the assessment should be performed as close as possible to the required schedule.

Regular tumor assessments should be performed in accordance to the guidelines in Section 5.5 to determine if PD is present.

The Treatment Period ends when a subject receives his or her last dose of study treatment; the subject then enters the Post-Treatment Period.

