6.3 Cabozantinib Dose Modifications, Interruptions, and Discontinuation

The following should be taken into consideration in decisions regarding dose modifications (reductions or interruption):

- As a general approach all AEs should be managed with supportive care at the earliest signs of toxicity considered related to the study treatment. Should this be ineffective, dose interruptions and/or reductions should be considered to prevent worsening of toxicity.
- The assigned starting dose for cabozantinib is 60 mg/day. 2 dose reduction levels of cabozantinib are permitted (see Table 6-2).
- Dose modification criteria for cabozantinib are shown in Table 6-3. Dose interruptions and/or reductions should be implemented for unacceptable toxicity. Doses may be modified at any time while a subject is on treatment.
- Dose reductions or interruptions may also occur in the setting of lower grade toxicity than defined in Table 6-3, if the investigator feels it is in the interest of a subject’s safety and will optimize drug tolerability.
- Interruption of cabozantinib treatment for cabozantinib-related AEs may occur at any time per investigator discretion. If treatment is interrupted due to related AEs for more than 6 weeks, cabozantinib should be discontinued unless there is unequivocal evidence that the subject is benefitting. In this situation, a subject may be able to restart therapy with a dose reduction upon resolution of the toxicity per the discretion of the investigator.
- Dose interruptions for reason(s) other than related AEs (eg, surgical procedures) can be longer than 6 weeks per the discretion of the investigator.

Guidelines for the management of specific AEs are provided in Section 6.3.3.

Table 6-2: Dose Reductions of Cabozantinib

Assigned Dose	First Dose Level Reduction	Second Dose Level Reduction
60-mg cabozantinib oral qd	40-mg cabozantinib oral qd	20-mg cabozantinib oral qd
40-mg cabozantinib oral qd	20-mg cabozantinib oral qd	No dose reduction permitted
20-mg cabozantinib oral qd	No dose reduction permitted	—

qd, once daily

Cabozantinib will be discontinued if a qd dose of 20-mg cabozantinib (minimum dose) is not tolerated

Table 6-3: Dose Modifications of Cabozantinib for Treatment-Related AEs

CTCAE v.4.0 Grade	Recommended Guidelines for Management ^a
Grade 1 AEs	Add supportive care as indicated. Continue cabozantinib treatment at the current dose level if AE is manageable and tolerable.

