Grade 1	Cabozantinib treatment may be continued at the current dose if PPES is clinically insignificant and tolerable. Otherwise, cabozantinib should be reduced to the next lower dose level. ^a Start urea 20% cream twice daily AND clobetasol 0.05% cream once daily. Reassess at least weekly; if PPES worsens at any time or does not improve after 2 weeks, proceed to the intervention guidelines for Grade 2.
Grade 2	Cabozantinib treatment may be continued if PPES is tolerated. Cabozantinib should be dose reduced or interrupted if PPES is intolerable. Continue urea 20% cream twice daily AND high potency steroid cream (eg, clobetasol 0.05%) once daily and add analgesics (eg, NSAIDs/gamma-aminobutyric acid agonists) for pain control if needed. Reassess at least weekly; if PPES worsens or affects self-care, proceed to the intervention guidelines for Grade 3.
Grade 3	Interrupt cabozantinib treatment until severity decreases to Grade 1 or 0. Continue treatment of skin reaction with high potency steroid cream (eg, clobetasol 0.05%) twice daily AND analgesics. Resume study drug at a reduced dose if PPES recovers to Grade \leq 1. Discontinue subject from study treatment if PPES does not improve within 6 weeks.

CTCAE, Common Terminology Criteria for Adverse Events; NSAID, non-steroidal anti-inflammatory drug; PPES, palmar plantar erythrodysesthesia syndrome.

^a Permitted dose levels are defined by individual protocols.

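### Does the plan leave the primary response scan undefined for patients who stop early or after a long dose hold?

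*Combined protocol and SAP*

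**What the plan says.** Section 9 defines the primary outcome as objective response at week 12. Eleven patients are accrued first, not counting screen failures. The trial stops if none responds; otherwise 6 more are accrued, and the null is rejected with 3 or more responses in 17.

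Section 5.5.1 (under 5.6) states which scan is used: "Only scans at week 12 (prior to surgery) will be used for purposes of the primary objective". On timing it says "This will be obtained after last dose of cabozantinib before surgical resection while waiting 28 days wash-out period". A week-6 scan is also taken, to look for rapid progression, but it does not enter the primary endpoint. Footnote n to Table 5-1 allows the post-treatment scan up to 28 after the last dose. No unit is printed; days is inferred from the 28-day wash-out. For assessments missed because of events outside the patient's control, Section 5.2 says "the assessment should be performed as close as possible to the required schedule".

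On stopping, Section 5.2 says "The Treatment Period ends when a subject receives his or her last dose of study treatment". Section 6.3 says "If treatment is interrupted due to related AEs for more than 6 weeks, cabozantinib should be discontinued unless there is unequivocal evidence" of benefit. Section 3 has a matching rule for toxicity that does not recover to a tolerable grade: "within 6 weeks, the subject will have study treatment discontinued unless there is unequivocal evidence that the subject is benefitting". Table 6-6 has one for hand-foot syndrome: "Discontinue subject from study treatment if PPES does not improve within 6 weeks". Section 3 also lists, among the reasons to stop, "Progressive disease (PD) or the subject no longer experiences clinical benefit as determined by the investigator".

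**The concern.** One scan appears to have two anchors: a calendar point (week 12) and the last dose. They agree for a patient dosed to the end and may separate for others.

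- **Stopped after a long hold.** By the time treatment is formally ended, the last dose is more than 42 days old and the 28-day limit has passed. The adverse-event rules in 8.1.1 run from the decision to discontinue; the scan has no such anchor.
- **Early stopper.** If week 12 means days 78 to 84, a patient whose last dose is on or before day 49 has an in-window scan no later than day 77. The word 'only' in Section 5.5.1 could then exclude it.
- **No scan.** Section 9 has no sentence making such a patient a non-responder.

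With 17 patients, one classification can separate 0 from 1 response at the first stage, or 2 from 3 at the end. An unwritten rule might be settled after the scan has been read.

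**Working it through.** **1. The plan's own figures.** Inputs from Section 9: n1 = 11, stop at 0 responses; n = 17, reject at 3 or more; p0 = 0.05, p1 = 0.24.

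P(reject) = Σ over x = 1 to 11 of P(X1 = x; 11, p) × P(X2 ≥ 3 − x; 6, p)

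- At p = 0.24: 0.1697 × 0.4422 + 0.2680 × 0.8073 + 0.5134 = 0.8048
- At p = 0.05: 0.3293 × 0.0328 + 0.0867 × 0.2649 + 0.0152 = 0.0490

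The stated power of 80% and type I error of 0.05 reproduce.

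**2. Timing after a hold.** 6 weeks = 42 days and 42 − 28 = 14, so the footnote limit closed more than 14 days before the stop. This part of the concern is correct.

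**3. What week 12 can mean.** Count the first dosing day as day 1. A patient who completes 12 weeks takes the last dose on about day 84. The scan comes after that dose and, by footnote n, by day 84 + 28 = 112, so between days 85 and 112. It never falls in days 78 to 84. A strict calendar reading would therefore exclude every fully compliant patient. Table 5-1 has no week-12 column; its only later pre-surgery column is keyed to the last dose. Section 12.4 sets quality of life and frailty at week 12, and Table 5-1 places both in that same column. Week 12 is thus a label for the post-treatment visit, and an early stopper has that visit too.

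**4. Late scan after a hold.** Section 5.3 sets a minimum of 28 days before surgery and no maximum. A scan at day 43 or later after the last dose, with surgery still to come, meets both conditions in Section 5.5.1. Only footnote n gives an upper limit, and it is worded as a permission.

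**5. No scan.** Both rules in Section 9 count responses among accrued patients. An undocumented response adds nothing, so the decision is the same whether or not the patient is called a non-responder. Only the denominator of the estimate could move: 3/17 = 17.6% (exact 95% interval 3.8% to 43.4%) against 3/16 = 18.8% (4.0% to 45.6%).

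**6. Effect of refusing scans.** Suppose k of the 17 patients (assumed; the documents give no rate) respond at the common rate p but their scans are refused, with positions split at random between the stages and the cut-offs kept. For k = 1 at 24%: (11/17) × 0.7669 + (6/17) × 0.7722 = 0.7688.

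| k | Power at 24% | Loss (points) | Type I error at 5% |
|---|---|---|---|
| 0 | 80.5% | – | 0.0490 |
| 1 | 76.9% | 3.6 | 0.0418 |
| 2 | 72.7% | 7.7 | 0.0353 |
| 3 | 68.0% | 12.4 | 0.0293 |

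If these patients never respond, every loss is 0.

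**7. Deciding with the result in view.** A non-response never adds to the count. Accepting only the favourable late scans therefore gives the same count as accepting all of them, with type I error 0.0490. With one post-treatment scan per patient, selective acceptance cannot raise the error above the design value.

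**8. How often the result is close.** At 24%, the chance of passing stage 1 and ending on exactly 2 or 3 responses is 0.1136 + 0.1957 = 0.3093. That is not an upper limit on how often one patient could matter. It omits stopping at 0 of 11 (0.0489) and one response in stage 1 followed by 3 or more in stage 2 (0.0261). The sum is 0.3843. The relevant size for one refused scan is the 3.6 points above, since that patient must also respond and be decisive.

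**The case for a change.** The strongest case for a change is that reading week 12 as a label does not help the patient stopped after a hold. Footnote n's limit has passed for that patient, the visit in Section 5.3 (within 14 days of the last dose) has passed too, and the week-6 scan is excluded. The clause in Section 5.2 on missed assessments says when to perform them, not whether a late result counts. In a trial decided by 3 responses in 17, a written rule would cost only a sentence or two.

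What stands is that no passage states that a late pre-surgery scan counts, and Section 9 has no explicit non-response sentence. The documents also do not say whether held time lies inside the 12 weeks. That is a question of treatment duration, on which no position is taken here, and it does not alter which scan is read.

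The rest is weaker. The group is small by construction: Sections 3 and 6.3 make an exception for patients with unequivocal benefit, who may restart and so acquire a new last dose and a new window. Those are the patients most likely to be responders. An early stopper with progression is not a responder on any reading. The response table has no row for unevaluated target lesions, but Section 5.5.1 refers evaluation to RECIST 1.1, so the omission carries little weight.

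**Conclusion.** No change to the plan follows. The early-stopper case rests on a calendar reading that would disqualify patients who complete treatment, and the no-scan case cannot affect either decision rule. What remains is missing detail for one uncommon situation: a patient taken off treatment after a hold of more than 42 days, without the benefit exception, and scanned late but before surgery. The natural handling is to use that pre-surgery scan and to count an accrued patient without one as a non-responder. It fits Section 5.5.1 and Section 9 as written and keeps the design's 80.5% power and 0.049 type I error.

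Refusing such scans would cost 3.6, 7.7 or 12.4 points of power for 1, 2 or 3 patients and would lower the type I error. These are high-side figures for those counts: they assume that the affected patients respond as often as the others, and the number affected is itself an assumption. The conclusion also rests on reading footnote n in days and on one post-treatment scan per patient.

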4 STUDY POPULATION

4.1 Inclusion Criteria

A subject must fully meet all of the following criteria to be eligible for the study:

1. Patients with renal mass consistent with a clinical stage \geq T3Nx or TanyN+ or deemed unresectable by surgeon;
2. Renal cell carcinoma with clear cell component on pre-treatment biopsy of the primary tumor;
3. The subject is \geq 18 years old on the day of consent;
4. ECOG performance status \leq 1
5. Patients must have adequate organ and marrow function, based upon meeting all of the following laboratory criteria within 14 days before first dose of study treatment:
 - Absolute neutrophil count (ANC) \geq 1500/mm³ (\geq 1.5 GI/L) without granulocyte colony-stimulating factor support.
 - White blood cell count \geq 2500/mm³ (\geq 2.5 GI/L).
 - Platelets \geq 100,000/mm³ (\geq 100 GI/L) without transfusion.
 - Hemoglobin \geq 9 g/dL.
 - Alanine aminotransferase (ALT), aspartate aminotransferase (AST), and alkaline phosphatase (ALP) \leq 3 x upper limit of normal (ULN). ALP \leq 5 x ULN with documented bone metastases.
 - Total bilirubin \leq 1.5 x ULN (for subjects with Gilbert's disease \leq 3 x ULN).
 - Serum albumin \geq 2.8 g/dl.
 - Serum creatinine \leq 1.5 x ULN or calculated creatinine clearance \geq 40 mL/min (\geq 0.67 mL/sec) using the Cockcroft-Gault equation:
 - Males: $(140 - \text{age}) \times \text{weight (kg)} / (\text{serum creatinine [mg/dL]} \times 72)$
 - Females: $[(140 - \text{age}) \times \text{weight (kg)} / (\text{serum creatinine [mg/dL]} \times 72)] \times 0.85$
 - Urine protein/creatinine ratio (UPCR) \leq 1 mg/mg (\leq 113.2 mg/mmol).

6. No hormonal therapy, chemotherapy, immunotherapy, or any other systemic therapy for a malignancy, in the 5 years prior to current study enrollment;
7. Sexually active fertile subjects and their partners must agree to use medically accepted methods of contraception (eg, barrier methods, including male condom, female condom, or diaphragm with spermicidal gel) during the course of the study and for 4 months after the last dose of study treatment;

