9 STATISTICAL CONSIDERATIONS

The primary outcome is objective response rate (complete and partial responses) at week 12 after the administration of cabozantinib. The Simon's two-stage design will be adopted for a possible early termination for futility. We hypothesize that there is > 24% response rate at 12-week and a rate < 5% will be considered as futility. In the first stage, 11 patients will be accrued (this does not include screen failures), and if there is no responses among them, the study will be stopped for futility. Otherwise, additional 6 patients will be accrued for a total of 17 patients. The null hypothesis will be rejected if there are 3 or more responses in 17 patients. The design yields a type I error rate of 0.05 and power of 80% when the true response rate is 24%. The final response rate will be estimated with 95% confidence interval by binomial test.

The safety profile of the treatment will be documented and summarized by summary statistics as frequency and percentage for each AE. We will do safety assesment after the first 6 patients without pausing the enrollment.

For disease free survival (DFS), which was defined as the interval between time of surgery and the first tumor recurrence, or death. Patients will be censored at time of last follow-up. For overall survival, death from any cause will be defined as the event. Patients will be censored at time of last follow-up. Overall survival (OS) and disease free survival (PFS) will be estimated

with the Kaplan-Meier method. The DFS and OS of each patient group at specific time points, such as 6 months, 1 year, and 3 year, etc. will be also estimated along with 95% CI.

For the biomarker study, descriptive statistics will be first used to summarize biomarker endpoints, including analyses of tumor biopsies. Biomarker data will also be displayed graphically, where appropriate. Depending on whether data is normally distributed, t-test or Wilcoxon rank sum test will be used to compare each biomarker between any two groups stratified by response or other factors, respectively. Logistics regression model will be further employed to test the adjusted effect of biomarker on the response rate after adjusting for other factors.

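### Nodal targets qualify on short axis but are summed on longest diameter, and the plan does not say whether its own text or RECIST 1.1 governs; close to a 30% decrease, the axis chosen can create or remove a partial response.

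*Combined protocol and SAP*

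**What the plan says.** The primary endpoint is set in Section 9: "The primary outcome is objective response rate (complete and partial responses) at week 12 after the administration of cabozantinib". Section 5.6 (Tumor Assessment, whose subsections are numbered 5.5.1 to 5.5.3) says response is to be judged by RECIST 1.1 and then writes out rules of its own:

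- **Which nodes may be targets (5.5.1):** "Lymph nodes must be at least 15mm in short axis to be included as a target lesion".
- **What is summed (5.5.1):** "A sum of the longest diameter for all target lesions will be calculated and reported as the baseline sum longest diameter". There is no exception for nodes.
- **Partial response (5.5.2):** "At least a 30% decrease in the sum of the longest diameter of target lesions, taking as reference the baseline sum longest diameter". Progression and stable disease refer to the same kind of sum.
- **Complete response of targets (5.5.2):** "The disappearance of all target lesions". No size is given at which a node counts as normal.

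Nodal disease is expected in some patients, because Section 4.1 admits "T3Nx or TanyN+ or deemed unresectable by surgeon". No section says which nodal axis is measured at week 12, or whether RECIST 1.1 or the written rules prevail if they differ.

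**The concern.** Nodes enter the target list on one dimension and are followed on another, under a standard that is named but not reproduced. A radiologist working from the written text sums longest diameters. A radiologist who takes the short-axis entry rule or the cited guideline as the guide may record short axes for nodes. If the two sums fall on opposite sides of a 30% decrease, the same scans give a responder under one and a non-responder under the other.

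The primary decision turns on very few patients. Section 9 rejects the null with 3 or more responses in 17 and stops for futility with none in the first 11. If the axis is settled only after week-12 measurements are known, the choice could be made with its effect on the count in view.

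**Working it through.** **1. The design as stated.** Inputs from Section 9: null rate 5%, target rate 24%, 11 patients in stage 1, stop if 0 respond, otherwise 6 more, reject with 3 or more of 17.

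P(reject | p) = sum over x = 1 to 11 of Bin(11, x, p) × P(Bin(6, p) ≥ max(0, 3 − x)).

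At p = 5% this is 0.0490, and at p = 24% it is 0.805. The stated 0.05 and 80% are reproduced.

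**2. What one patient is worth.** One of 17 is 5.9 percentage points.

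- 3/17 = 17.6% (exact 95% CI 3.8% to 43.4%): null rejected.
- 2/17 = 11.8% (exact 95% CI 1.5% to 36.4%): not rejected.
- In stage 1, 0/11 stops the trial and 1/11 continues it.

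**3. The two sums on the same lesions.** Let P be the primary's longest diameter and L and S a node's long and short axes, with 0 for baseline and 1 for week 12.

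- As written: (P1 + ΣL1)/(P0 + ΣL0) − 1
- Short axis for nodes: (P1 + ΣS1)/(P0 + ΣS0) − 1

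The documents give no nodal sizes, so all nodal dimensions are assumed, as are the 80 mm primaries. The 72 to 53 mm primary borrows the median tumor sizes before and after treatment (7.2 and 5.3 cm) in the presurgical sunitinib series described in Section 1. Those are cohort medians on another drug, used only as a plausible scale. All sizes are in mm.

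| Case | Primary | Node(s), long × short | Sum as written | Short axis for nodes |
|---|---|---|---|---|
| A | 72 to 53 | two, 30×20 to 20×10 | 132 to 93, −29.5% (SD) | 112 to 73, −34.8% (PR) |
| B | 72 to 53 | one, 30×20 to 20×10 | 102 to 73, −28.4% (SD) | 92 to 63, −31.5% (PR) |
| C | 80 to 55 | one, 30×20 to 21×16 | 110 to 76, −30.9% (PR) | 100 to 71, −29.0% (SD) |
| D | 72 to 53 | two, 30×20 to 20×13.3 | 132 to 93, −29.5% (SD) | 112 to 79.7, −28.9% (SD) |
| E | 80 to 63 | one, 30×20 to 12×8 | 110 to 75, −31.8% (PR) | 100 to 71, −29.0% (SD) |

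In A to C the node changes shape and the category changes, upward or downward. D is A with the nodes' shape kept, and the category does not change. E shows a further route: the node keeps its shape but shrinks 60% while the primary shrinks 21%, and the two sums give that node different weight. If every lesion shrinks by the same fraction s, both formulas reduce to −s.

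**4. How wide the sensitive zone is.** Take an 80 mm primary and one 30×20 mm node. The shrinkage of the primary needed to reach −30% overall is:

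- Node −10% long, −40% short: as written 1 − (0.7×110 − 27)/80 = 37.5%; short axis 1 − (0.7×100 − 12)/80 = 27.5%.
- Node −40% long, −10% short: as written 1 − (77 − 18)/80 = 26.3%; short axis 1 − (70 − 18)/80 = 35.0%.
- Node −30% in both: 30.0% under either rule.

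**5. The complete-response wording.** Suppose an 80 mm primary vanishes and a node's longest diameter goes from 25 to 12 mm. The sum goes from 105 to 12, or −88.6%. As written this is a partial response, which still counts in the objective response rate.

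**The case against.** **No outright contradiction.** A short-axis entry threshold and a longest-diameter sum are separate steps, and the written response categories all use the same sum. No sentence tells anyone to add short axes. This stands: a reader might infer that the section contradicts itself, and it does not. The defect is an unranked pair of authorities (a named standard and a set of written rules) together with a change of axis that is not explained.

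**RECIST 1.1 is named, so it governs.** The bullets could be read as a summary of the standard. That is reasonable, but the plan does not say it, and its written sum covers all targets without exception. Equally, the documents do not reproduce RECIST 1.1, so this point does not assert from them that the written sum departs from it.

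**The example is close to the line.** In case A the threshold is 0.7 × 132 = 92.4 mm and the sum is 93 mm, a miss of 0.6 mm. The change of category also depends on assumed nodes that lose half of their short axis and a third of their long axis. This stands as a limit on how often the problem arises. It does not remove it, since case C goes the other way with different sizes.

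**Few patients may be exposed.** Section 4.1 also admits patients through T stage or unresectability, and a positive node below 15 mm in short axis is not a target. This stands too: the exposed share of the 17 is unknown.

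**Conclusion.** The point holds in a limited form and is worth correcting. For a patient who has a nodal target and a total change near −30%, uneven nodal shrinkage can make the choice of axis create or remove a partial response. The direction is not fixed. The frequency cannot be estimated, because the documents give neither the share of patients with nodal targets nor any nodal dimensions. The importance comes from the decision rule, under which one reclassified patient can separate 3/17 from 2/17.

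Three stronger readings are not supported:

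- **That the type I error is inflated or the sample size is wrong.** The stated design reproduces. Large error rates appear only if one supplies a share of node-positive patients and a rate of one-way misclassification. For example, 50% and 20% would give a type I error of 0.449. The documents supply neither figure, and the cases above move both ways.
- **That the written rule systematically understates response.** Cases C and E gain a partial response under it.
- **That requiring nodes to disappear lowers the objective response rate.** It mainly moves a patient from complete to partial response. Both count, so it affects the reported complete response rate and hardly the primary endpoint.

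**What to change.** Before any week-12 scan is classified, amend 5.5.1 and 5.5.2:

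1. Define the sum of diameters as the longest diameter of non-nodal targets plus the short axis of nodal targets, the axis already used to qualify them. Use it at baseline and at follow-up.
2. Apply that one sum to partial response, stable disease and progression.
3. State that RECIST 1.1 governs wherever the written text differs, and check the new wording against the cited guideline.

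As a secondary change, replace disappearance for nodal targets in the complete-response rule with the nodal size criterion of the named standard. This keeps the reported complete response rate interpretable.

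A minor tidy-up, not part of this point: the overall-response table shows no row for target partial response with non-target complete response. Check it in the source document and add it if it is absent.

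The cost is an amendment to wording and to the measurement worksheet. No scans, patients or changes to the design are needed.
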